4.6.3. Clinical Laboratory Evaluation

Unless otherwise specified, all the safety lab endpoints will be conducted on safety estimand. Safety analyses for the double-blind period will be conducted using the SS1. For overall study safety, including double-blind period, open-label period, and safety follow-up period, summary statistics will be provided using the SS2.

All laboratory data will be reported in SI units. Selected laboratory measures will also be reported using CN units. Values that are outside of reference ranges will be flagged as high (H) or low (L) in the listings. Descriptive summaries by treatment and by nominal visit will be provided for the baseline (with respect to the treatment period) and postbaseline values as well as the change from baseline values.

Observed and change from baseline values for selected measurements for each visit will be displayed graphically for patients who have both a baseline and a postbaseline planned measurement. Unplanned measurements will be excluded from graphs.

Shift tables will be produced for selected measurements. A shift table will include unplanned measurements. The shift table will include the number and percentage of patients within each baseline category (low, normal, high, or missing) versus each postbaseline category (low, normal, high, or missing) by treatment. The proportion of patients shifted will be compared between treatments.

For qualitative laboratory analytes, the number and percentage of patients with abnormal values will be summarized by treatment. All analyses should be conducted from baseline to Week 30, and from baseline to safety follow-up.

A listing of abnormal findings will be created for laboratory analyte measurements, including qualitative measures. The listing will include patient ID, treatment group, laboratory collection date, study day, analyte name, and analyte finding.

For the serum lipid levels including total cholesterol, low density lipoprotein (LDL), high density lipoprotein (HDL), very low-density lipoprotein (VLDL) and triglycerides, an MMRM as described in Section 4.1.5.1 using safety estimand, will be used to fit the changes from baseline at each scheduled postbaseline visits for double-blind period using SS1 and for overall study (including double-blind period, open-label period, and safety follow-up period) using the SS2. Both units will be analyzed using log transformation.

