4.1.4. Treatment Groups

Participants are randomized in 3 treatment arms. During the double-blind study period these intervention arms are Placebo, TZP 5 mg, and TZP 10 mg. During the open-label period there are only 2 interventions: TZP 5 mg and TZP 10 mg.

For the purposes of tables, figures, and listings, during the double-blind study period, the treatment groups will be Placebo, TZP 5 mg, TZP 10 mg, and TZP_ALL (pooled tirzepatide doses). Placebo will be the reference treatment across all statistical reports whenever the treatment effect is compared between TZP 5 mg, TZP 10 mg, TZP ALL, and placebo.

Up to Week 52 or up to safety follow-up treatment will be expressed in the tables, figures, and listings as TZP_ALL (representing pooled arm of TZP 5 mg/5 mg, TZP 10 mg/10 mg), TZP 10 mg (representing TZP 10 mg/10 mg), TZP 5 mg (representing TZP 5 mg/5 mg), and Placebo/TZP 5 mg (representing placebo/TZP 5 mg). There is no comparison between any of these treatment groups at Week 52.

Within-treatment comparisons between different scheduled visits such as Weeks 30 and 52 for parameters such as HbA1c change (and others) from baseline may be performed.

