4.6. Safety Analyses

The definitions of AE, SAE, and product complaint can be found in Section 10.3, Appendix 3 of Protocol GPGV.

AEs will be coded from the actual term using MedDRA and reported with PTs and SOC. Selected notable AEs of interest may be reported using HLTs or SMQs.

A TEAE is an untoward medical occurrence that emerges during a defined treatment period, having been absent pretreatment, or worsens relative to the pretreatment state, and does not necessarily have to have a causal relationship with the treatment. For events with a missing severity during the baseline period, it will be treated as "mild" in severity for determining treatment emergence. Events with a missing severity during the postbaseline period will be treated as "severe" and treatment emergence will be determined by comparing with baseline severity.

In general, the baseline of a TEAE is defined as an event prior to first dose of randomized study treatment (tirzepatide or placebo). MedDRA LLT will be used in the treatment-emergent derivation. The maximum severity for each LLT during the baseline period, including ongoing medical history, will be used as baseline severity.

For participants who are randomized to placebo/tirzepatide 5 mg treatment arm at Week 0, the baseline for overall study safety (including all treatment periods and follow-up period) will be defined as:

- for TEAE: an event starts prior to and is ongoing at the time of the first dose of tirzepatide.
- for lab/vitals/ECG categorical analyses: the last non-missing observation collected prior to the time of first dose of tirzepatide.

Unless specified otherwise, safety assessments will be guided by the *safety estimand* setting comparing safety of tirzepatide doses with placebo irrespective of adherence to study intervention or initiation of rescue therapy. Safety analyses for the double-blind period will be conducted using the SS1. For overall study safety, including double-blind period, open-label period, and safety follow-up period, summary statistics will be provided using the SS2.

Percentages of participants with TE abnormal, high, or low laboratory measures at any time will be summarized and compared between treatment groups using Fisher's exact test.

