A TE high value is defined as a change from a value less than or equal to the high limit at baseline to a value greater than the high limit at any time during double-blind period, open-label period, and safety follow-up. A TE low result is defined as a change from a value greater than or equal to the low limit at baseline to a value less than the low limit at any time during double-blind period, open-label period, and safety follow-up. High and low laboratory limits will be determined by the central laboratory reference ranges.

Values and change from baseline to postbaseline values of central laboratory measures, vital signs, and selected ECG parameters will be summarized at each scheduled visit. The analysis model to make comparisons among treatment groups, relative to continuous change from baseline values assessed over time can be found in Section 4.1.5.4.

For special safety topics, in case of a smaller number of events, a listing will be provided instead of summary table.

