4.6.6.1. Hypoglycemic Events

Definitions and information on hypoglycemia are provided in Section 8.3.3.1 of Protocol GPGV.

Total hypoglycemia includes any event that meets criteria for documented symptomatic, severe, asymptomatic, or unspecified (that is, missing symptoms or signs, but with a blood glucose, BG, <70 or <54 mg/dL) whether daytime or nocturnal. Those categories that are defined by BG will be analyzed by the BG <70 and <54 mg/dL thresholds separately.

Total hypoglycemia category will have the following 2 subcategories:

- events with BG < 70 mg/dL included, and
- events with BG <54 mg/dL included.

To avoid duplicate reporting, all consecutive BG values <70 mg/dL (3.9 mmol/L) occurring within a 1-hour period may be considered as a single hypoglycemic event.

SS1 will be used for the primary analysis for hypoglycemia during Week 0 through Week 30, and SS2 for Week 0 through end of the treatment period (Week 52).

The incidence of hypoglycemic episodes will be summarized for each treatment group for 0 to 30 weeks, and 0 to the end of the treatment period. The summary includes the number of patients and percent of patients reporting hypoglycemic episodes. Fisher's exact test will be used for treatment comparison.

Counts of hypoglycemia or the rate of incidence of hypoglycemia episodes may be analyzed as described in Section 4.1.5.4 with a negative binomial regression model. The results will also be reported for the subset of participants who have baseline basal insulin use. All these analyses will be conducted excluding data after initiation of new antihyperglycemic therapy.

A listing of the individual hypoglycemic episodes will be presented from baseline to the end of the treatment period using SS2. Additional exploratory analyses may be performed if deemed necessary.

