4.9. Changes to Protocol-Planned Analyses

Refer to revision history.

5. Sample Size Determination

The statistical power calculation assumes that the evaluation of superiority of pooled tirzepatide 5 mg and 10 mg QW against placebo will be conducted at a 2-sided significance level of 0.05, relative to the primary endpoint (change in HbA1c from baseline at 30 weeks) in an analysis utilizing all data, on or off intervention. Additionally, it assumes a 1.1% greater mean reduction in HbA1c (placebo adjusted) for pooled tirzepatide (5 mg and 10 mg) at Week 30 visit, and a common SD of 1.5% from change in HbA1c at Week 30 visit.

Based on these assumptions, randomizing at least 90 participants in a 1:1:1 ratio to each study arm will provide 90% power to demonstrate superiority of the pooled tirzepatide 5 mg and 10 mg to placebo.

6. Supporting Documentation

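### The SAP contradicts itself on whether between-arm laboratory and hypoglycemia tests extend past Week 30; if they do, the laboratory contrast is biased and the hypoglycemia contrast diluted

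*SAP*

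**What the plan says.** Text that confines comparison to the double-blind period:

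- SAP 4.1.4, on the groups reported to Week 52 or safety follow-up: "There is no comparison between any of these treatment groups at Week 52".
- SAP 4.1.2 assigns the comparison of tirzepatide with placebo to SS1, the double-blind data.
- SAP 4.6 and the opening of 4.6.3 offer only summary statistics for the overall study on SS2. SAP 4.1.5.4 offers descriptive statistics for event counts over the overall study.
- SAP 4.6.2 restricts Fisher's test in the adverse-event overview to the double-blind period.

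Text that does not:

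- SAP 4.6 says that percentages with treatment-emergent (TE) abnormal, high or low values "at any time will be summarized and compared between treatment groups using Fisher's exact test". Its TE high definition requires a value "greater than the high limit at any time during double-blind period, open-label period, and safety follow-up", and the TE low definition has the same window. Protocol 9.3.4.3 pairs test and window in the same way.
- SAP 4.6.3 says of shift tables: "The proportion of patients shifted will be compared between treatments". The next paragraph adds: "All analyses should be conducted from baseline to Week 30, and from baseline to safety follow-up". No test is named; Fisher's follows only from the default for categorical safety endpoints in 4.1.5.4.
- SAP 4.6.6.1: "The incidence of hypoglycemic episodes will be summarized for each treatment group for 0 to 30 weeks, and 0 to the end of the treatment", meaning Week 52. A Fisher sentence with no period limit follows shortly after.

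For overall-study laboratory categories, the placebo/tirzepatide arm takes as baseline "the last non-missing observation collected prior to the time of first dose of tirzepatide" (SAP 4.6). SAP Table GPGV.3.1 restricts those SS2 analyses to participants with at least one tirzepatide dose.

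**The concern.** A programmer working from 4.6, 4.6.3 and 4.6.6.1 alone would produce between-arm p-values that cover the open-label and follow-up periods. A programmer working from 4.1.2 and 4.1.4 would not. Both would be following the SAP.

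If the laboratory text is followed, the placebo/tirzepatide arm differs from the tirzepatide arms in four ways: it is on tirzepatide, its baseline is reset to about Week 30, it has fewer scheduled draws in which to show an abnormality, and it has lost anyone who left before open-label dosing. Any-time incidence rises with the number of draws, so the tirzepatide arms would tend to show an excess with no drug effect.

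For hypoglycemia the error runs the other way. The placebo arm spends 22 of the 52 weeks on tirzepatide, so a real excess shrinks, and a non-significant 52-week result could be read as reassurance in a pediatric safety report.

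**Working it through.** **Arm sizes.** SAP Section 5 plans 90 randomized 1:1:1, which is 60 pooled tirzepatide v 30 placebo. Its stated 90% power (difference 1.1, SD 1.5, two-sided 0.05) reproduces at 90.7% by the normal approximation and 90.0% by noncentral t. That figure is not in question; it only supplies the arm sizes used below.

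**Scheduled post-baseline draws to safety follow-up** (Protocol 1.3.1 and 1.3.2), taking Visit 13 (Week 30) as the reset baseline:

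| Tests | Tirzepatide arms | Placebo/tirzepatide |
|---|---|---|
| Hematology, chemistry, lipids, eGFR | 6 (Weeks 8, 16, 30, 42, 52, 56) | 3 (Weeks 42, 52, 56) |
| HbA1c, serum glucose | 8 (also Weeks 4 and 12) | 3 |
| Lipase, pancreatic amylase, calcitonin | 5 (Weeks 16, 30, 42, 52, 56) | 3 |

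**Incidence with no drug effect.** With k independent draws and abnormal probability p per draw, any-time incidence is 1 − (1 − p)^k. The documents give no p, so every value here is an assumption. At p = 3%:

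- 6 draws: 1 − 0.97^6 = 16.7%
- 3 draws: 1 − 0.97^3 = 8.7%
- ratio 1.9; with latent within-participant correlation of 0.3 to 0.5, 1.8 to 1.6

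**Fisher false-positive rate.** Exact enumeration of the two-sided test at 0.05, no drug effect, 6 v 3 draws, 60 v 30 participants (correlated columns use a beta-binomial model):

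| p per draw | Incidence, independent | Rejection, independent | Incidence, correlation 0.3 | Rejection, correlation 0.3 |
|---|---|---|---|---|
| 2% | 11.4% v 5.9% | 6.9% | 6.5% v 4.4% | 1.8% |
| 5% | 26.5% v 14.3% | 22% | 15.7% v 10.8% | 5.3% |
| 10% | 46.9% v 27.1% | 40% | 29.4% v 20.8% | 11% |
| 15% | 62.3% v 38.6% | 55% | 41.2% v 30.1% | 14% |

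At p = 3% the rejection rate is 10.7% with independent draws and 7.4% to 5.4% with latent correlation 0.3 to 0.5. At p = 1% it is about 1%. For a single dose v placebo (30 v 30), independent draws give 13% at p = 5% and 26% at p = 10%. With equal incidence in both groups, as equal draws and a common baseline give when there is no drug effect, Fisher's test never exceeds 5%; for 60 v 30 the highest value found was 4.3%.

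**Hypoglycemia.** There is no baseline reset, and all arms are counted from Week 0, so with no drug effect the 52-week test rejects about 4% of the time. With a drug effect, assume 30-week risks of 15% v 6% and constant hazards:

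- tirzepatide over 52 weeks: 1 − 0.85^(52/30) = 24.5%
- placebo then tirzepatide: 1 − 0.94 × 0.85^(22/30) = 16.6%
- risk ratio: 15/6 = 2.5 at Week 30, against 24.5/16.6 = 1.5 at Week 52

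With assumed rates of 0.6 v 0.2 per year instead, the rate ratio falls from 3.0 to 0.6 / [(0.2 × 30 + 0.6 × 22)/52] = 1.6, and the power of Fisher's test (60 v 30) falls from 48% to 22%.

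**The case against.** The best reply is that the SAP, read as a whole, already makes SS2 descriptive. Sections 4.1.2, 4.1.4, 4.6 and the opening of 4.6.3 all point that way. The version 3 entry in the history table says the Week 52 model statements were dropped from 4.1.5.3 and 4.1.5.4 because there is no treatment comparison then, and 4.1.5.4 is the safety section. A TE definition spanning three periods does not itself order a test over all three, since on SS1 the data end with the double-blind period. The sentence running all analyses to follow-up can cover descriptive tables. Restricting SS2 laboratory categories to tirzepatide-treated participants also suggests an exposure summary and not a placebo contrast.

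This stands as evidence of intent, and it defeats the stronger reading. A reader might infer that the sponsor has settled on testing past Week 30; the documents show conflicting instructions, not a settled plan. It does not remove the conflict. The laboratory and hypoglycemia Fisher sentences name no analysis set or period, where the adverse-event overview does, and 4.1.4 speaks of Week 52 while 4.6.3 runs to follow-up at Week 56.

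Three further limits are fair. The valid Week 30 comparisons are planned regardless, and 4.6.6.1 names SS1 as primary for hypoglycemia. Safety tests carry no multiplicity control (SAP 2.1). A comparison of 5 mg with 10 mg on SS2 would have neither the reset nor the draw imbalance.

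**Conclusion.** The SAP is internally inconsistent on between-arm safety tests after Week 30, and one of the two readings yields misleading p-values.

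For laboratory categories, that reading biases any-time incidence upward in the tirzepatide arms relative to placebo/tirzepatide. The direction follows from the draw schedule (3 v 6, 3 v 8 or 3 v 5) and holds for scheduled draws with the same per-draw rate in all arms. The size rests on assumed rates: over the values tried for the 6 v 3 panels at 60 v 30, false-positive rates run from below 5% (rare or strongly clustered abnormalities) to well above it (common, independent ones). Unplanned measurements, which the shift tables include, are not modelled.

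A reader might also infer that none of these p-values would measure a drug effect. For hypoglycemia that goes too far: the 52-week test keeps its size and estimates early against delayed start, which understates the contrast with placebo. Nor is the placebo arm's draw count half that of the other arms for every test; that ratio fits hematology, chemistry, lipids and eGFR only.

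The primary efficacy analysis is unaffected.

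**What to change.** In SAP 4.6, 4.6.3 and 4.6.6.1, state that between-arm tests use SS1 only and, for laboratory values, that the TE window for those tests ends at Week 30. This matches the limit that 4.6.2 sets for the adverse-event overview. In 4.6.3, name the test intended for shifts. State that SS2 laboratory and hypoglycemia outputs are descriptive, giving counts and percentages with exposure-adjusted rates if wanted, in line with 4.1.4. The three-period TE definition can stay for those SS2 summaries.

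The cost is wording. No data, visits or sample size change, and the only outputs lost are p-values that 4.1.2 and 4.1.4 already appear to exclude.

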#### Visit 17 Clinic Visit

Clinic visit procedures are like those in the double-blind period EXCEPT fasting is not required at this visit.

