# Early Termination and Safety Follow-up Visit

The participant will arrive at the clinic in a fasted state for Early Termination Visit. Safety Follow-up Visit is a non-fasted visit.

Participant and parent or legal guardian must return study equipment and devices (e-diary and glucometer) to the investigative site.

Participants discontinuing the study early should have the follow-up visit approximately 30 days after the early termination visit and should have a follow-up visual acuity check and dilated fundoscopic examination performed by an eye care professional (ophthalmologist or optometrist) within + 21 days of the early termination visit. If the early termination visit is scheduled within 6 months of the previous visual acuity check and dilated fundoscopic examination are not needed.

Participants who discontinue the study before randomization do not need to complete this visit.

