# **Clinical Laboratory Tests**

Hematology	
	Assayed by Lilly-designated laboratory
Hemoglobin	
Hematocrit	
Erythrocyte count (RBCs - red blood cells)	
Mean cell volume	
Mean cell hemoglobin concentration	
Leukocytes (WBCs - white blood cells)	
Differential:	
Neutrophils, segmented	
Lymphocytes	
Monocytes	
Eosinophils	
Basophils	
Platelets	
Cell morphology (RBCs and WBCs)	
Clinical Chemistry	Assayed by Lilly-designated laboratory
Sodium	
Potassium	
Bicarbonate	
Total bilirubin	
Direct bilirubin	
Alkaline phosphatase (ALP)	
Alanine aminotransferase (ALT)	
Aspartate aminotransferase (AST)	
Gamma-glutamyl transferase (GGT)	
Blood urea nitrogen (BUN)	
Creatinine	
Uric acid	
Calcium	

Glucose	
Special Chemistry	Assayed by Lilly-designated laboratory
HbA1c	
Insulin	Results will not be provided to the investigative sites
C-peptide	Results will not be provided to the investigative sites
Calcitonin	
Thyroid-stimulating hormone (TSH)	
Thyroxine (T4, free)	
Biomarkers	Assayed by Lilly-designated laboratory. Results will not be provided to the investigative sites
Adiponectin, total	
Proinsulin, intact	
Glucagon	
Lipid Panel	Assayed by Lilly-designated laboratory
Total cholesterol	
Low density lipoprotein (LDL)	Value will be calculated. If triglycerides are >400mg/dL, the direct LDL will be assayed
High density lipoprotein (HDL)	
Very low density lipoprotein (VLDL)	
Triglycerides	
Hormones (female)	
Serum pregnancy	Assayed by Lilly-designated laboratory
Urine pregnancy	Evaluated locally at study site
Urine Chemistry	Assayed by Lilly-designated laboratory
Albumin	
Creatinine	
Pancreas (Exocrine panel)	Assayed by Lilly-designated laboratory
Pancreatic amylase	
Lipase	
Calculations	Will be calculated by the central laboratory and included in laboratory result reports

eGFR (CKD-EPI)	
Urinary albumin/creatinine ratio	
Pharmacokinetic Samples for Tirzepatide	Assayed by Lilly-designated laboratory. Results will not be provided to the investigative sites
Genetics Sample	Assayed by Lilly-designated laboratory. Results will not be provided to the investigative sites
Exploratory Biomarker Stored Samples	Assayed by Lilly-designated laboratory. Results will not be provided to the investigative sites
Serum	
Plasma (EDTA)	
Plasma (P800)	
Immunogenicity Samples	Assayed by Lilly-designated laboratory
Islet Cell Antibody 2 (IA2)	
GAD65	
Tirzepatide anti-drug antibody	Results will not be provided to the investigative sites

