 To compare 5 mg, and 10 mg tirzepatide QW, analyzed as pooled and separate treatment arms, to placebo at 30 weeks, and To assess the effect of 5 mg and 10 mg tirzepatide QW, analyzed as pooled and separate treatment arms at 52 weeks 	 Incidence of new or worsening of dyslipidemia Incidence of new or worsening of hypertension Incidence of new or worsening of albuminuria Incidence of new or worsening of diabetic neuropathy Incidence of new or worsening of diabetic retinopathy or diabetic maculopathy in either eye 	
To assess safety of 5 and 10 mg tirzepatide QW, analyzed as pooled and separate treatment arms, at 30 weeks and through end of the safety follow-up period	 Treatment-emergent adverse events Discontinuation of study intervention due to AEs Adjudicated pancreatic AEs Serum calcitonin Incidence of allergic, hypersensitivity reactions, and injection site reactions Incidence of treatment-emergent anti-drug antibodies to tirzepatide Percentage change from baseline for serum lipid levels Change in systolic and diastolic blood pressure and heart rate from baseline Occurrence of hypoglycemic events Incidence of initiation of rescue therapy for severe-persistent hyperglycemia 	
 To compare 5 and 10 mg tirzepatide QW, analyzed as pooled and separate treatment arms, to placebo at 30 weeks, and To assess the effect of 5 and 10 mg tirzepatide QW, analyzed as pooled and separate treatment arms, at 52 weeks or end of the safety follow-up period 	 Change from baseline for physical and developmental measures height height SDS and weight SDS height velocity Tanner Staging 	
Characterize the pharmacokinetics and pharmacodynamic relationships of tirzepatide	Relationship between tirzepatide exposure and key safety and efficacy measures	
To assess the effect of 5 and 10 mg tirzepatide QW, analyzed as pooled and separate treatment arms, on patient-reported outcomes at 30 and 52 weeks	 Change from baseline for PedsQL Generic Core Scales PedsQL (3.2) Diabetic Module from baseline 	

Objectives	Endpoints
Tertiary/Exploratory	
 To compare 5 mg and 10 mg tirzepatide QW, analyzed as pooled and separate treatment arms, to placebo at 30 weeks, and To assess the effect of 5 mg and 10 mg tirzepatide QW, analyzed as pooled and separate treatment arms, at 52 weeks 	 Incidence of HbA1c ≤6.5% without clinically significant (blood glucose <54 mg/dL) or severe hypoglycemia Incidence of HbA1c <7.0% without clinically significant (blood glucose <54 mg/dL) or severe hypoglycemia

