4.6.6.13. Dyslipidemia

An incidence of new dyslipidemia is defined by 1 of the following 2 conditions:

- a new AE of dyslipidemia reported, or
- at least 2 consecutive values of LDL ≥130 mg/dL or fasting TG ≥150 mg/dL on separate visits after randomization measured by central laboratory in an individual with normal LDL and TG at baseline.

The worsening of an existing dyslipidemia is defined by one of the following conditions:

- AE of dyslipidemia with worsening severity compared to previous MH or AE reported, or
- at least 2 consecutive values of LDL ≥130 mg/dL or fasting TG ≥150 mg/dL on separate visits after randomization measured by central laboratory in an individual with previous history of dyslipidemia and normal LDL and TG at baseline, or
- at least 2 consecutive values of LDL or fasting TG at least 5 mg/dL above baseline on separate visits after randomization measured by central laboratory in an individual with LDL ≥130 mg/dL or TG ≥150 mg/dL at baseline.

The incidence of new or worsening of dyslipidemia will be summarized by treatment, using SS1 from baseline to Week 30, and using SS2 from baseline to Week 52. The AE of dyslipidemia will be searched using narrow PTs in *Dyslipidaemia* SMQ (20000026).

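### The overall-study lipid model compares non-fasting samples at Week 42 and the safety follow-up visit with a fasting baseline, and the SAP has no fasting filter or label

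*SAP*

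**What the plan says.** SAP 4.6.3 covers total cholesterol, LDL, HDL, VLDL and triglycerides. It specifies an MMRM under the safety estimand to "fit the changes from baseline at each scheduled postbaseline visits for double-blind period using SS1 and for overall study". The second of the two models covers the whole study, "including double-blind period, open-label period, and safety follow-up period) using the SS2. Both units will be analyzed using log transformation". The section does not mention fasting status.

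The protocol's Schedules of Activities (1.3.1 and 1.3.2) place the lipid panel at V3, V7, V9 and V13 in the double-blind period, and at V17, V19, early termination and V801 afterwards. In the later schedule the fasting row marks only V19 and early termination. Protocol 4.1.1 agrees. Of Visit 17 it says: "Clinic visit procedures are like those in the double-blind period EXCEPT fasting is not required at this visit". Of the last visit it says: "Safety Follow-up Visit is a non-fasted visit".

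Appendix 2 of the protocol (10.2) says of LDL: "Value will be calculated. If triglycerides are >400mg/dL, the direct LDL will be assayed".

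SAP 1.1 lists "Percentage change from baseline for serum lipid levels" among the additional secondary endpoints, for Week 30 and for the period up to the end of safety follow-up.

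Fasting status does appear in SAP 4.6.6.13, where one route to new dyslipidemia is "at least 2 consecutive values of LDL ≥130 mg/dL or fasting TG ≥150 mg/dL on separate visits after randomization".

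**The concern.** A change from baseline is interpretable when both samples are taken under the same conditions. Triglycerides respond to a recent meal. LDL is calculated, so a triglyceride shift can pass into it, and VLDL may be affected in the same way. The SAP itself treats fasting as material when it classifies dyslipidemia, but not when it models lipid change.

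No comparison between arms removes the problem after Week 30. All participants then receive tirzepatide, and SAP 4.1.4 rules out comparisons between treatment groups at Week 52. Results are read within arm, so a feeding effect common to all arms stays in each arm's estimate. At stake is how the lipid course after Week 30 is read: a benefit on triglycerides could look smaller at Week 42 than it is, and a rise at V801 could be taken wholly as an effect of stopping the drug.

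**Working it through.** The plan states no figure for this point, so there is none to reproduce. The check sets the lipid row of the schedules against the fasting row.

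| Scheduled lipid draw | Fasting visit? |
|---|---|
| Week 0 (V3, baseline) | Yes |
| Week 8 (V7) | Yes |
| Week 16 (V9) | Yes |
| Week 30 (V13) | Yes |
| Week 42 (V17) | Not required |
| Week 52 (V19) | Yes |
| Week 56 (V801) | No |

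The early termination visit is also a fasting draw. Some repeats of the double-blind header lack the Week 30 fasting mark and others show it; I take the gap as a fault of text conversion.

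**Count.** There are 6 scheduled post-baseline lipid visits, of which 4 are fasting and 2 are not. After Week 30, 2 of 3 are not fasting.

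**Baseline.** SAP 4.1.1 takes the last value from Visit 1 to Visit 3. The only scheduled lipid panel in that span is at V3, a fasting visit.

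**Possible size at Week 42.** Two inputs are assumptions, since the documents give neither: fed triglycerides are (1 + f) times fasting, with f from 10% to 30%, and the true change on drug is -20%. With log-transformed data, the apparent change if all samples are fed is 0.80 × (1 + f) - 1:

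- f = 10%: 0.80 × 1.10 - 1 = -12%
- f = 20%: 0.80 × 1.20 - 1 = -4%
- f = 30%: 0.80 × 1.30 - 1 = +4%

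If only a share p of samples is fed, the multiplier becomes (1 + f) to the power p. The estimate then lies between -20% (p = 0) and the values above (p = 1). The SAP does not provide for estimating p.

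**Calculated LDL.** The protocol does not give the equation. If it subtracts triglycerides divided by 5 (assumption) and fasting triglycerides are 150 mg/dL (assumption), the fed excess is 15 to 45 mg/dL, and LDL would read 15/5 = 3 to 45/5 = 9 mg/dL too low. VLDL would read too high by the same amount if it is obtained from the same term, which the protocol does not say.

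**V801.** No on-drug figure applies here. Protocol 4.1.1 has tirzepatide stop at V19 and background diabetes medication adjusted then. From Week 52 to Week 56 is 28 days; with the half-life of about 5 days given in protocol section 2, that is 28/5 = 5.6 half-lives. A change between V19 and V801 therefore combines loss of drug, changed background therapy and the move from a fasted to a fed sample.

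**Dyslipidemia rule.** Successive scheduled draws that are both fasting are Weeks 8-16 and 16-30. The later neighbouring pairs (30-42, 42-52) each include Week 42, where fasting is not required. Whether Weeks 30 and 52 are consecutive depends on whether a non-fasting Week 42 value is passed over, and SAP 4.6.6.13 does not say. Separately, SAP 4.6 resets the baseline for categorical laboratory analyses to the last value before first tirzepatide in the placebo arm, while 4.6.6.13 counts visits from randomization.

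**The case against.** The strongest reply is that little depends on these two visits. Lipids are additional secondary endpoints outside type I error control. Every double-blind draw is fasting, so the Week 30 comparison with placebo stands. Week 52 is fasting to fasting, and the treatment-by-visit term gives it its own mean. All of this is right, and it limits the point to Week 42 and V801. It is also right that fasting at Week 42 is optional, not excluded, and that the size of any shift is assumed. Protocol 4.1.1 does have a general sentence about arriving fasted for clinic visits, but the visit-specific text and the fasting row override it for V17 and V801.

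A reader might infer more than the documents support:

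- *That open-label lipid results as a whole are affected.* Only Week 42 is; Week 52 is a fasting visit.
- *That the lipid objective in SAP 1.1 depends only on a non-fasted value.* It describes a window up to the end of follow-up, and that window includes Week 52.
- *That participants who switch from placebo can never meet the triglyceride criterion.* Section 4.6.6.13 counts from randomization, so the pairs 8-16 and 16-30 exist, and arguably 30-52. Fasted samples at Week 42, adverse event reports and the LDL criterion can also qualify. Under the reset baseline in SAP 4.6 the scheduled fasting values on tirzepatide would be too few, but that is an ambiguity to settle, not an established zero.

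**Conclusion.** The point holds for two visits and for triglycerides, with VLDL and calculated LDL affected so far as they depend on triglycerides. The mismatch of fasting status follows directly from the schedules and SAP 4.6.3 and needs no assumption. The direction and size of the resulting shift do rest on assumptions: over the assumed range for f, an all-fed Week 42 would overstate the triglyceride ratio to baseline by 10% to 30%, and a mixed Week 42 by less. For V801 the documents support only the statement that feeding, drug withdrawal and changed background therapy cannot be separated. No primary, key secondary or Week 30 conclusion changes. The correction is still worth making, because it removes an avoidable bias from within-arm estimates that have no control to absorb it.

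**What to change.** In SAP 4.6.3, restrict the change-from-baseline models for triglycerides, VLDL and calculated LDL to the fasting visits (Weeks 8, 16, 30 and 52). Summarise the Week 42 and V801 values of these three lipids descriptively, labelled non-fasting.

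In SAP 4.6.6.13, add one sentence on whether fasting triglyceride values at Weeks 30 and 52 count as consecutive when Week 42 is not fasting. Add another on which baseline applies to participants who switch from placebo, so that it agrees with SAP 4.6.

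SAP 1.1 needs no change, and neither does any visit or procedure. The cost is SAP wording and a visit filter. The one loss is that these three lipids would have no modelled estimate at Week 42 or V801.
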